# Synopsis

Sponsor / Sponsor- Investigator	[name]. med. [name]., MPH; Department of Endocrinology, Diabetes and Clinical Nutrition; University Department of Internal Medicine, Kantonsspital Aarau, [name]	
Study Title:	Full Title: Effect of Early Nutritional Therapy on Frailty, Functional Outcomes and Recovery of Undernourished Medical Inpatients Trial: The EFFORT Project	
Short Title	The EFFORT trial	
Protocol Version	EKNZ 2014_001 (version 3.3, 27.3.2014)	
Trial registration:	This trial will be registered at www.ClinicalTrials.gov	
Study category and Rationale	Category A (nutritional products used are authorised in Switzerland and the application is done according to the specialised information	
Clinical Phase:	Confirmation study regarding effectiveness and safety of nutritional therapy in medical inpatients	
Background and Rationale:	Illness is associated with appetite loss leading to relevant nutritional deficits, particularly in elderly, frail medical inpatients. Undernutrition is associated with morbidity, long hospital stays and costs. Despite these associations, benefit of providing early nutritional therapy to unselected medical inpatients at risk for undernutrition remains largely unproven due to lack of large-scale, high-quality randomized controlled trials (RCTs). Therefore, a large conclusive trial is urgently needed to answer the questions (a) whether or not appetite loss during acute illness is indeed a protective physiological response that should be tolerated; (b) which patients do or do not benefit from nutritional therapy; (c) how and why nutrition affects the course of disease from a mechanistic physio-pathological standpoint.	
Objective(s):	To test the hypothesis that in medical inpatients at risk for undernutrition defined by the nutritional risk score (NRS 2002), early tailored nutritional therapy to reach nutritional targets based on individualized nutritional counseling is a cost-effective strategy to prevent mortality, morbidity and functional decline.	
Outcome(s):	The primary composite endpoint is combined adverse outcome within 30 days defined as (a) all-cause mortality, (b) admission to the intensive care unit from the medical ward, (c) major complications, (d) unplanned hospital readmissions and (d) decline in functional outcome from admission to day 30 assessed by Barthel's index (-10%). Secondary endpoints include (a) each single component of the primary endpoint (b) short-term nutritional and functional outcomes from inclusion to day 10 or hospital discharge; (c) hospital outcomes; (d) 30-day and 180-day outcomes (e) Other safety endpoints including adverse gastrointestinal effects associated with nutritional therapy assessed daily until hospital discharge.	
Study design:	Randomized controlled trial	
Inclusion / Exclusion criteria:	Unselected adult medical inpatients at risk of undernutrition [NRS≥3 points] and an expected hospital stay of ≥5 days who are willing to provide informed consent will be included. We will exclude patients in critical care or post-operative state, unable to swallow, at long-term need for parenteral/enteral nutrition, in terminal condition, pregnant, with acute pancreatitis or acute liver failure, with anorexia nervosa, that were earlier included into the trial	

Measurements and procedures:	Patients in the intervention group will receive individualized nutritional therapy to reach nutritional targets (caloric, protein, micronutrients, other) based on a predefined nutritional strategy. In control patients, according to patients' appetite, standard hospital nutrition will be served. Nutritional therapy may be started in control patients, if any sort of swallowing disorders develops or if patients need to be prepared for operation. All patients will be re-assessed daily during the hospital stay for nutritional intake and nutritional therapy may be escalated every 24-48 hours (food fortification, oral supplements, enteral, parenteral nutrition) if targets are not met (at least 75% of targets).		
Study Product / Intervention:	Different nutritional products (oral nutritional supplements, enteral nutrition, parenteral nutrition) to reach nutritional targets		
Control Intervention:	Usual care;		
Number of Participants with Rationale:	The inclusion of 2000-3000 patients will provide 78-90% power to detect a reduction in the primary endpoint of 15% (from 40% to 34%)		
Study Duration:	After a 3 month pilot (feasibility period), other centers will be stepwise included for a total duration of 3 years, or until the total sample size is included.		
Study Schedule:	05/2014Year of First-Participant-In (planned) 05/2017 Year of Last-Participant-Out (planned)		
Investigator(s):	This project is embedded in multiple research national and international collaborations with nutritional experts. The RCT will be conducted in multiple experienced Swiss centers and possibly international sites. The Clinical Trial Unit (CTU) of the University of Basel will provide logistical and statistical support.		
Study Centre(s):	Single-centre or multi-centre. If multi-centre note number of projected centres to be involved. Or countries if multi-national study		
Outlook and discussion	Important gaps in the literature and the controversy about nutritional therapy in critical illness call into question our current nutritional therapy approach in medical inpatients. Herein, integrating recognized international experts and generating novel data both from the current literature and state-of-the-art investigation involving thousands of patients, we aim to establish an evidence-based standard for nutritional strategy for acutely-ill medical inpatients. This strategy will be tested in the largest nutritional RCT yet outside critical care and will allow us to answer whether, why, how, and where nutritional therapy works. This "real-world" comparative effectiveness research project thus has the potential to provide conclusive evidence about nutritional therapy in unselected, acutely-ill hospitalized, often polymorbid and frail medical inpatients to facilitate informed decision-making by patients and healthcare professionals world-wide.		
GCP Statement:	This study will be conducted in compliance with the protocol, the current version of the Declaration of Helsinki, the ICH-GCP or ISO EN 14155 (as far as applicable) as well as all national legal and regulatory requirements.		

# **ABBREVIATIONS**

AE Adverse Event

BMI body mass index

BMR Basal metabolic rate (BMR)

BIA Body impedance
CRF Case Report Form
CTU Clinical trial unit

eCRF Electronic Case Report Form

FAACT Functional Assessment Anorexia-Cancer Therapy

GCP Good Clinical Practice

GI Gastro-intestinal

IIT Investigator-initiated Trial

IL Interleukin

ITT Intention to treat

ONS Oral nutrition supplement

PI Principal Investigator

QoL Quality-of-life

RCT Randomised controlled trial SOP Standard Operating Procedure

TNF Tumor nekrosis factor

LOS length-of-stay

# 1. Study Administration and legal aspects

# 1.1. Role of funding

This trial is supported by the Swiss National Science Foundation (SNSF Professorship, PP00P3\_150531 / 1). Additional funding will be requested from hospital Institutions (ie, Kantonsspital Aarau) and Industrial partners.

# 1.2. Statistical analysis

For the statistical analysis, the investigators will closely collaborate with the clinical trial unit of the University of Basel ([name] and [name] [name], CTU, University of Basel, Basel, Switzerland).

# 1.3. Study registration

The study will be registered at the ClinicalTrials.gov website.

# 1.4. Categorisation of the study

This trial correspond to the Category A because the different nutritional products used are authorised in Switzerland and the application is done according to the specialised information.

#### 1.5. Competent Ethics Committee and ethical conduct of the study

The main ethical committee will be the EKNZ (Leitethikkomission, EKNZ 2014 001).

The responsible investigator at each site ensures that approval from an appropriately constituted Competent Ethics Committee is sought for the clinical study.

All changes in the research activity and all unanticipated problems involving risks to humans will be reported to the all ethical committees within 48 hours. Premature study end or interruption of the study is reported within 15 days. The regular end of the study is reported to the CEC within 90 days, the final study report shall be submitted within one year after study end.

The study will be carried out in accordance to the protocol and with principles enunciated in the current version of the Declaration of Helsinki, the guidelines of Good Clinical Practice (GCP) issued by ICH, in case of medical device: the European Directive on medical devices 93/42/EEC and the ISO Norm 14155 and ISO 14971, the Swiss Law and Swiss regulatory authority's requirements. The CEC and regulatory authorities will receive annual safety and interim reports and be informed about study stop/end in agreement with local requirements.

#### 1.6. Declaration of interest

All coinvestigators will declare their conflict of interest as appropriate.

#### 1.7. Patient information and informed consent

The investigators or other authorised individuals personal will explain to each participant the nature of the study, its purpose, the procedures involved, the expected duration, the potential risks and benefits and any discomfort it may entail. Each participant will be informed that the participation in the study is voluntary and that he/she may withdraw from the study at any time and that withdrawal of consent will not affect his/her subsequent medical assistance and treatment.

The participant must be informed that his/her medical records may be examined by authorised individuals other than their treating physician. All participants for the study will be provided a participant information sheet and a consent form describing the study and providing sufficient information for participant to make an informed decision about their participation in the study. The patient information sheet and the consent form will be submitted to the ethical review board to be reviewed and approved. The formal consent of a participant, using the approved consent form, must be obtained before the participant is submitted to any study procedure.

The participant should read and consider the statement before signing and dating the informed consent form, and should be given a copy of the signed document. The consent form must also be signed and dated by the investigator (or his designee) and it will be retained as part of the study records.

The investigator affirms and upholds the principle of the participant's right to privacy and that they shall comply with applicable privacy laws. Especially, anonymity of the participants shall be guaranteed when presenting the data at scientific meetings or publishing them in scientific journals.

Individual subject medical information obtained as a result of this study is considered confidential and disclosure to third parties is prohibited. Subject confidentiality will be further ensured by utilising subject identification code numbers to correspond to treatment data in the computer files.

For data verification purposes, authorised representatives of the Sponsor (-Investigator), a competent authority or an ethics committee may require direct access to parts of the medical records relevant to the study, including participants' medical history.

# 1.8. Early study termination

The Sponsor-Investigator may terminate the study prematurely according to certain circumstances, for example:

- ethical concerns,
- insufficient participant recruitment,
- when the safety of the participants is doubtful or at risk, respectively,
- alterations in accepted clinical practice that make the continuation of a clinical trial unwise,
- early evidence of benefit or harm of the experimental intervention

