# 4. Design of the trial

# 4.1. Study design

This is an investigator-initiated, randomised controlled superiority trial with an open intervention comparing the effects of a nutritional intervention with a usual care control group.

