#### 8.3. Sample Size considerations

This study is designed to show superiority of nutritional therapy compared to "appetite-guided" standard care regarding the composite primary endpoint. Our hypothesis is that early nutritional therapy will reduce mortality and morbidity within a follow up period of 30 days after the index hospitalization. From preliminary observational data collected during the TRIAGE pilot study, we estimate that 40% of the target patient population (NRS ≥3 points and LOS ≥5days) will reach the primary endpoint within 30 days (10% mortality, 5% ICU admission from the hospital ward, 15% complications, 10% functional decline with 10% reaching more than 1 endpoint). We hypothesize that our nutritional intervention will decrease this risk by an absolute number of 6% (relative decrease of 15%), i.e., from 40% to 34%. For a comparison of two independent binomial proportions using Pearson's Chi-square statistic with a Chi-square approximation with a two-sided significance level of 0.05, a sample size of 1'359 per group achieves a power of at least 0.9 when the proportions are 0.4 and 0.34.

Thus, a total number of 2000-3000 patients will provide the study with a power of 78-90% to detect a 15% relative decrease in the risk to reach the primary endpoint. The table below shows sample sizes for different assumptions regarding effectiveness of our intervention and power.

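### The target sample size is a range of 2000-3000, and 1.8 lets the sponsor-investigator stop for early benefit with no boundary, so the plan permits, but does not schedule, outcome-driven stopping against a single unadjusted 0.05 test

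*Protocol*

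**What the plan says.** - **Size.** The synopsis states: "The inclusion of 2000-3000 patients will provide 78-90% power". Section 8.3 repeats it: "a total number of 2000-3000 patients will provide the study with a power of 78-90" per cent. The calculation behind it is a single point: "a sample size of 1'359 per group achieves a power of at least 0.9 when the proportions are 0.4 and 0.34", that is 2718 in total. Section 15 (Potential limitations) discusses recruiting 3000.
- **End of recruitment.** The synopsis sets three years "or until the total sample size is included". Sections 8.4 and 14 also cap enrolment at three years. No section turns the total sample size into one number or says what decides where in the range to stop.
- **Early termination.** Section 1.8 gives the sponsor-investigator the decision and lists examples of grounds. Most concern ethics, recruitment, safety or changes in practice. The last is "early evidence of benefit or harm of the experimental intervention".
- **Test.** Section 8.2 plans one chi-square comparison of the arms. Section 8.3 sizes it with a "Chi-square approximation with a two-sided significance level of 0.05".
- **Access and oversight.** The trial is a "randomised controlled superiority trial with an open intervention". Blinded assessment is promised for days 30 and 180 (6.2). Section 1.5 mentions annual safety and interim reports to the ethics committee and authorities, without saying whether they show results by arm. The DSMB appears only as a recipient of SUSAR reports (9.2).

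**The concern.** A 0.05 test keeps its nominal size when it is done once, at a point not chosen from the results. Here two features leave that point open. The target is a span of 1000 patients, and benefit is an express ground for stopping early, held by the sponsor-investigator in an open trial. If a favourable interim result ended the trial and were then judged at 0.05, the false-benefit rate would exceed 2.5% and the estimated effect would tend to be too large. Even if nothing of the kind happened, a positive result at, say, 2200 patients could not be defended from the protocol alone against the charge that the end was chosen on the data.

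**Working it through.** **1. Reproduce the plan's figure.** Inputs from 8.3: p1 = 0.40, p2 = 0.34, two-sided alpha 0.05, power 0.90, 1:1 allocation (4.3). Mean proportion 0.37.

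n per group = [1.96 x sqrt(2 x 0.37 x 0.63) + 1.2816 x sqrt(0.40 x 0.60 + 0.34 x 0.66)]^2 / 0.06^2 = 1358.6, rounded up to **1359**. This matches, and all nine rows of the table in 8.3 reproduce as well.

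**2. Power across the range.** Power = Phi{[0.06 - 1.96 x sqrt(0.4662/n)] / sqrt(0.4644/n)}, with n per group.

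| Total N | n per group | Power |
|---|---|---|
| 2000 | 1000 | 79.4% |
| 2718 | 1359 | 90.0% |
| 3000 | 1500 | 92.6% |

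The stated 90% therefore belongs to 2718, not to the top of the range. The stated 78% at 2000 is met only with a continuity correction (78.1%). With that correction 3000 gives 92.0%, so no single formula gives 78% and 90% at the two ends. This is an imprecise power statement, not an error-rate problem.

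**3. What outcome-driven stopping would do.** The protocol schedules no looks, so the look times here are **assumptions**. Under no effect, the test statistics at sizes n1 < n2 are jointly normal with correlation sqrt(n1/n2); for 2000 and 3000 this is sqrt(2/3) = 0.816. The rule matches what is at issue: the trial ends early only if Z > 1.96 in favour of the intervention, and the final test is two-sided at 0.05.

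- False-benefit rate = P(Z > 1.96 at any look).
- Total type I error = false-benefit rate + P(final Z < -1.96 with no earlier stop). The second term is 2.50%, because almost no path crosses upward early and ends below -1.96.

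| Assumed looks | False-benefit rate | Total type I error |
|---|---|---|
| one test only | 2.50% | 5.00% |
| 2000, 3000 | 3.85% | 6.35% |
| 2000, 2500, 3000 | 4.35% | 6.85% |
| 1000, 2000, 3000 | 5.36% | 7.86% |

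These come from the joint normal distribution and agree with simulation. Unrounded, the first two rows with interim looks lie just below the halfway point, so to one decimal they are 3.8% and 6.3%, then 4.3% and 6.8%.

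**4. What a boundary would do.** One halfway look at two-sided p < 0.001 (|Z| > 3.29), with the final test left at 0.05, gives an overall error of 5.02%. A halfway O'Brien-Fleming rule at 3000 (interim p < 0.0052, final p < 0.048) holds 5.0%; power at a 0.048 final level is 92.3%, against 92.6% with no interim look.

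**The case against.** The best defence is that no data-dependent rule is written. Section 1.8 reads like a template list of examples, no look is scheduled, and the single test in 8.2 has its nominal size if done as written. This stands. A reader might infer that the 0.05 level is already lost. The documents do not support that; they show a permission without a control.

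A reader might also infer that the range of N itself inflates the error. It does not if time, money or recruitment decides the end, and the limits the protocol does state (three years, or full enrolment) are of that kind. No section links the stopping size to results, but none excludes the link either.

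A third tempting step is to quote 7.7%, 8.7% or 10.7% for the same three look schedules. Those figures count early crossings in both directions. Stopping for harm is not the issue here, so the benefit-only figures are the relevant ones, and they too rest on assumed looks.

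The open design should not be stretched. Patients and caregivers are unblinded, day-30 and day-180 assessment is blinded, and the trials unit secures the randomisation. Nothing says that the sponsor-investigator sees pooled outcomes by arm. Equally, nothing prevents it, and in-hospital events accrue in view of unblinded staff.

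Finally, a boundary may sit in a SAP or DSMB charter that is not shown, and its mere absence from the protocol would be no fault. But the target N and the benefit ground are in the protocol, and are stated loosely there. Section 8.2 requires the SAP only before database closure, so it need not exist before an early look.

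**Conclusion.** The point holds as a weakness of wording with a real but conditional consequence. The protocol has no single target N: its sections give 2000-3000 and 3000, and its calculation implies 2718. It also grants an early-benefit stop with no rule attached. Used as written, that permission would raise the false-benefit rate above 2.5%, to roughly 3.8-5.4% under the assumed looks, and total type I error to roughly 6.3-7.9%. These sizes rest on three assumptions: the look times, a 0.05 trigger in favour of the intervention, and a two-sided final test at 0.05. If no one with authority to stop sees outcomes by arm, there is no inflation, and what remains is a power statement spanning 79.4% to 92.6%. The change should be made, but the design is not invalid without it.

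**What to change.** 1. In 8.3 and the synopsis, name one target N with its power: 2718 gives 90.0% and 3000 gives 92.6%. The protocol states no allowance for loss to follow-up, so 2718 carries none. Align section 15 with the choice. If 2000 is kept as a fallback, report its power as 79.4% by the method used for the table.
2. State that recruitment may end before the target only on calendar or recruitment grounds, decided without knowledge of outcomes by arm.
3. In 1.8, either delete benefit as a ground, or allow it only on the DSMB's advice under a boundary fixed before any look. One halfway look at p < 0.001 is an example that keeps the overall error at about 5.0%; other standard boundaries would also serve. Leave the harm and safety grounds unchanged.

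The cost is protocol wording and practically no power. The sponsor loses some freedom over when to end recruitment, and a trial that closes below the target would have to be reported as short of it.

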# 2. Background and rational

Acute and chronic illness is associated with loss of appetite and body weight, which increases the risk for undernutrition, particularly in the elderly and frail medical patient population. This relationship between acute disease and eating behavior / nutritional status may well be bi-directional, with illness affecting nutritional status, but also dietary factors influencing the course of illness. For example, cytokines, such as interleukin (IL)-6 and tumor-necrosis-factor (TNF)-alpha, affect brain circuitries that control food intake, delayed gastric emptying and skeletal muscle catabolism. Whether loss of appetite associated with acute illness is indeed a protective physiological response or a therapeutic target needing early corrective nutritional therapy is debated. Such controversy over the benefits and optimal protocols of nutritional therapy can only be resolved with a large randomised-controlled trial (RCT) comparing early nutritional therapy with "appetite-guided" nutrition in this population.

Undernutrition is common in elderly, chronic and/or polymorbid inpatients and associated with detrimental metabolic consequences, such as catabolism and muscle wasting. Undernutrition *per se* is associated with higher mortality and morbidity, increased risk for infection and an increased hospital length-of-stay (LOS). Despite a shortfall of evidence that nutritional therapy actually alters clinical outcomes, these relationships have led to the current clinical approach of providing nutritional therapy early to medical inpatients at risk for undernutrition as an empiric strategy to combat undernutrition and associated adverse outcomes. However, apart from critical care, where large trials recently have been published, there is an important lack of high-quality data from large RCTs in acutely-ill medical inpatients to shed light on the optimal type, caloric amount and timing of such therapy.

Smaller trials have investigated the effects of nutritional strategies on selected patient outcomes, mainly changes in body weight and nutrition-specific quality of life (*Table 1*). Some trials suggested that clinical outcomes are improved by nutritional therapy in regard to risk of infections, complications, lengths of hospital stay, functional status (activities of daily living), quality of life and even mortality. However, most trials were highly heterogeneous in design, patient populations and type of interventions, lacked statistical power to demonstrate safety and together, produced inconclusive results. Unsurprisingly, two previous aggregate data meta-analyses confirm the important lack of high-quality evidence to endorse or refute nutritional support. Both meta-analyses, however, were based on aggregate data only and did not specifically examine the effect of early nutritional therapy in medical inpatients. Rather, one meta-analysis focused on such therapy in critical care/perioperative patients, while the other only considered general protein and energy supplementation in the elderly. Moreover, having been published in 2007 and 2009, respectively, neither meta-analysis captures the most recent work. We are currently performing an up-to-date meta-analysis based on aggregate data and individual patient data (IPD), to provide a solid evidence base for the development of a "state-of-the-art" nutritional therapy strategy, which will be tested in the largest yet randomized controlled intervention trial outside critical care.

